4 RANDOMIZATION AND BLINDING

4.1 Randomization

Eligible patients will be centrally randomized in a 2:1 ratio to receive CDX-011 or capecitabine. For subjects enrolled in the study under protocol amendments 3 and 4, the randomization will be stratified by the following factors:

- 0-1 prior line of chemotherapy for advanced disease vs. 2 prior lines of chemotherapy for advanced disease
- Progression-free interval ≤ 6 months after receipt of taxane therapy vs. progression-free interval > 6 months after receipt of taxane therapy
- Received anthracycline therapy previously vs. no prior anthracycline therapy

There are no subjects enrolled under the original protocol. In protocol amendments 1 and 2, different stratification factors are considered. Specifically,

- Strata Under Amendment 1:
 - No lines of prior chemotherapy for advanced disease vs. 1 line prior chemotherapy for advanced disease – 0 vs. 1
 - “Resistant” to anthracycline therapy (i.e., progression-free interval of ≤ 6 months after completing treatment) vs. “Exposed” to anthracycline therapy (i.e., progression-free interval of > 6 months after completing treatment).

- Strata Under Amendment 2 and 2.1:
 - 0-1 prior line of chemotherapy for advanced disease vs. 2 prior lines of chemotherapy for advanced disease
 - “Resistant” to anthracycline therapy (i.e., progression-free interval of ≤ 6 months after completing treatment) vs. “Exposed” to anthracycline therapy (i.e., progression-free interval of > 6 months after completing treatment).

In the stratified analysis for this study, the stratification factors in Amendment 3 will be used. Given the changes in protocol amendments in stratification factors, the primary analysis of efficacy will be based on the actual stratification factors that are corrected after randomization. In addition, the secondary analysis using the *stratification factors as randomized* will also be performed, with the following mapping approach:

- All patients randomized under Amendment 1 will be considered as 0-1 prior line of chemotherapy for advanced disease.
- All patients randomized under Amendment 1 and 2.1 will be considered as received anthracycline therapy previously.
- For all patients randomized under Amendment 1 and 2.1, their Progression-free interval after receipt of taxane therapy will be determined based on the actual data reported in the clinical database.

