Scales/Items	Number of Items	Item Range	Item Numbers
Global health status			
Global health status	2	6	29, 30
Functional scales			
Physical functioning	5	3	1 to 5
Role functioning	2	3	6, 7
Emotional functioning	4	3	21 to 24
Cognitive functioning	2	3	20, 25
Social functioning	2	3	26, 27
Symptom scales/items			
Fatigue	3	3	10, 12, 18
Nausea and vomiting	2	3	14, 15
Pain	2	3	9, 19
Dyspnea	1	3	8
Insomnia	1	3	11
Appetite loss	1	3	13
Constipation	1	3	16
Diarrhea	1	3	17
Financial difficulties	1	3	28

Baseline HRQOL assessments will be administered to patients prior to randomization. Post-baseline HRQOL assessments are planned for Day 1 of Cycles 3, 5, 7, etc. (i.e., “odd cycles”) and End of Treatment (EOT) visit.

Summarization of the HRQOL data will be based on the actual study visits (including unscheduled visits and EOT visits) mapped at Weeks 6, 12, 18, etc.

If multiple HRQOL assessments are associated with the same time point, the assessment performed closest to the planned study day will be used for purposes of summarizing the data. If 2 measurements are equidistant from the planned study day, the measurement occurring prior to the planned study day will be used for summarization.

The primary HRQOL analysis will be based on the subset of patients in the ITT population who complete the HRQOL questionnaire at baseline.

Missing assessments present a challenge in analyzing and interpreting HRQOL data, especially when the data are missing non-randomly. For example, patients who experience increased toxicity or disease progression, hospice entry, or death are more likely to miss one or more assessments. Similarly, in a longitudinal study data may be missing at later assessments because of death or withdrawal due to disease progression. This leaves purportedly healthier patients, with better HRQOL scores on study longer and displaying a misleading trajectory of higher scores over time. If the reasons for missing data are ignored and the analyses are based only on the observed data, the estimates may be biased in that they do not accurately reflect the entire population of study patients ([Troxe1 1998](#))

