The initial HRQOL analysis will evaluate the EORTC QLQ-C30 scores (global health status and each individual function/symptom scale) longitudinally using a linear mixed effects model for repeated measures. This model, which assumes missing data are MAR, will describe the rate of change in HRQOL scores over time for each treatment arm, taking into account the between-patient variability by incorporating each patient's individual starting point and individual rate of change. The MIXED procedure in SAS will be used with patients as the random effect; treatment arm will be defined as the fixed effect. The model also will include linear time effects (i.e., week) and time by treatment interaction terms. A covariance structure that follows an autoregressive (AR) process dependent only on the prior HRQOL assessment will be used (i.e., AR-1). If there is model convergence issue, then compound symmetry covariance structure will be used.

Because missing HRQOL data are anticipated to be related to worsening prognosis, a sensitivity analysis will be performed using a pattern-mixture model to assist in the analysis of potentially non-ignorable missing data. For this analysis, patients will be stratified into groups based on their treatment arm and timing of study dropout for HRQOL assessment (anticipated to be largely due to disease progression and death). Patients will be classified as “dropouts” if their last HRQOL assessment was prior to 6 months and as “completers” if their last assessment was 6 months or later. Mixed effects models will be created within each stratum, which will provide for separate estimates of treatment effect for “dropouts” and “completers”. Parameter estimates for each stratum will then be combined into a weighted average for the entire treatment arm. As noted previously, selected demographics and disease characteristics also will be summarized for “dropouts” and “completers” separately to evaluate if the missing HRQOL data are MAR.

A check of the distributional assumptions for the longitudinal models will be performed, along with diagnostics to examine residuals and the presence of any outlying and influential observations. The results from the data checking and model diagnostics will be presented in a separate report.

The HRQOL objective is considered exploratory. For all HRQOL scales, the p-values will be evaluated in an exploratory manner using a nominal significance level of 0.05 (2-sided).

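### The exploratory HRQOL mixed model gives each arm its own starting mean and omits the randomization strata, giving up a modest amount of precision that the pre-randomization baseline score would supply

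*SAP*

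**What the plan says.** SAP 10.7 makes patient the random effect and states that "treatment arm will be defined as the fixed effect". It then says: "The model also will include linear time effects (i.e., week) and time by treatment interaction terms". The model is meant to reflect each patient's "individual starting point and individual rate of change". Residual covariance is AR(1), with a fallback: "If there is model convergence issue, then compound symmetry covariance structure will be used". No other fixed terms are listed.

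On the baseline score, the same section says: "Baseline HRQOL assessments will be administered to patients prior to randomization". It also fixes the analysis set: "The primary HRQOL analysis will be based on the subset of patients in the ITT population who complete the HRQOL questionnaire at baseline".

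On the strata, SAP 4.1 says "the randomization will be stratified by the following factors" and lists three binary factors: prior lines for advanced disease, progression-free interval after taxane, and prior anthracycline. It takes the Amendment 3 factors for stratified analyses and the corrected values for the primary efficacy analysis. PFS (SAP 10.3.1), ORR (10.4) and OS (10.6) are all compared with stratified tests.

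HRQOL is exploratory, with nominal two-sided 0.05 p-values and no multiplicity adjustment (SAP 10.1 and 10.7).

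**The concern.** With arm as a free fixed effect, the model estimates a separate week-0 mean in each arm. If the baseline score is taken before randomization, the true difference between those means is zero, and the model spends information estimating it. The estimated starting difference and the estimated slope difference are negatively correlated. A chance baseline imbalance therefore pulls the slope contrast the other way, and that noise is carried in its standard error. The individual starting point does not prevent this: a random intercept is neither a baseline covariate nor a shared arm mean.

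The strata are known for every randomized patient and used for PFS, ORR and OS, but are left out here without a stated reason.

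At stake is some precision in the HRQOL comparisons. The SAP also leaves two points open that programmers could settle differently: whether week 0 is in the response vector, and which questionnaire is the baseline.

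**Working it through.** **The plan's own figure.** The only sample-size figure is for PFS. With hazard ratio 4.0/6.25 = 0.64, 2:1 allocation, two-sided 0.05 and 85% power, events = (1.960 + 1.036)² / [(2/3)(1/3)(ln 0.64)²] = 8.978 / (0.2222 × 0.1992) = 202.9, so 203 as stated. No figure is given for HRQOL.

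**Inputs from the documents.** 200 and 100 patients; scores at week 0 and every six weeks; planned PFS medians of 6.25 and 4.0 months; the fixed terms, random effect and AR(1) structure of SAP 10.7.

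**Assumptions not in the documents.** Week 0 is a response. Visits run to week 48. HRQOL attrition is exponential at the planned PFS medians: weekly rate ln 2/(6.25 × 52/12) = 0.0256 on CDX-011 and ln 2/(4.0 × 52/12) = 0.0400 on capecitabine. Random intercept and random slope are independent. Variances are as listed below.

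**Formula.** For a patient last seen at visit k, X has columns 1, week, week × arm and arm. V = (intercept variance)·11ᵀ + (slope variance)·ttᵀ + (residual variance)·AR(1). Information is the sum over arms and k of n × P(last visit = k) × XᵀV⁻¹X. Inverting the 4 × 4 matrix gives the SAP model. Deleting the arm column and inverting the 3 × 3 matrix gives the common-mean model. The ratio of slope-contrast variances equals 1 − r², where r is the correlation between the estimated starting difference and the estimated slope difference in the SAP model.

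**Common baseline mean, variances in points, AR(1) 0.3:**

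| Intercept var. | Residual var. | Slope SD per week | SAP model | Common mean | Ratio | r |
|---|---|---|---|---|---|---|
| 200 | 200 | 0.2 | 0.00753 | 0.00649 | 0.861 | −0.37 |
| 250 | 150 | 0.5 | 0.01271 | 0.01191 | 0.937 | −0.25 |
| 300 | 100 | 1.0 | 0.02832 | 0.02775 | 0.980 | −0.14 |

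Over this range the variance falls by 2-14%.

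**Common baseline mean, wider range.** With a random-intercept share of baseline variance of 0.4-0.7, slope SD over 24 weeks of 0-1 baseline SD, and AR(1) of 0-0.6 per six weeks, the ratio runs from 0.796 to 0.973, a reduction of about 3-20%.

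Together the two ranges give roughly 2-20% of the variance. On the standard error that is 1 − √0.98 = 1% to 1 − √0.80 = 11%.

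**Strata main effects.** If the strata explain 10% of baseline variance, the slope-contrast ratio over the wider range is 0.976-0.999, a reduction of 0.1-2.4%. A random intercept already absorbs most of what they would explain. With both changes the ratio is 0.74-0.97.

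**Which score is the baseline.** SAP 10.7 puts it before randomization. SAP 7.6, unless specified otherwise, takes the nearest value not later than first dose. Table 1 schedules the questionnaire at screening and again at Cycle 1 Day 1, waived if done within the previous 24 hours (footnote 7). Randomization may precede treatment by up to 5 days (footnote 25), and the trial is open-label. Under the general rule, the baseline could be a score given after the patient knows the assigned arm. Only the pre-randomization score justifies a common mean.

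**The case against.** The strongest reply is that the loss is small, the analysis is exploratory and the comparison is already valid. That stands. Under the model's own assumptions the slope contrast is unbiased, and variation from chance baseline imbalance is already in its standard error. Omitting strata tends to make standard errors conservative.

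A reader might infer that randomized balance is discarded. It is not: allocation is balanced whatever model is fitted, and what is lost is efficiency.

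A reader might also infer a much larger loss. If only post-baseline scores were responses and the target were the week-12 difference in level, conditioning on baseline would cut the variance by 41-58% under similar assumptions. A common mean would cut the variance of a week-24 level difference by 6-71%. Neither is the contrast SAP 10.7 describes, which is rate of change with an individual starting point for each patient. That wording implies week 0 is a response, although the SAP should say so.

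Two objections bear on the remedy. A common mean is unsafe if the baseline can be a Cycle 1 Day 1 score after open-label assignment. Nor does it carry over to the pattern-mixture analysis, whose groups are defined by arm and post-randomization dropout timing: randomization does not equalize baseline means between arms within them. Both stand, and both limit the change proposed.

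**Conclusion.** The point holds as a modest, avoidable loss of precision in the initial HRQOL model. With week 0 as a response, sharing one pre-randomization baseline mean would reduce the variance of the week-by-treatment contrast by roughly 2-20%. Strata main effects alone would reduce it by about 0.1-2.4%, so the case for them is mainly consistency with PFS, ORR and OS. These sizes depend on assumed variances, attrition at the planned PFS medians and, for the strata, 10% of baseline variance explained; the documents supply no HRQOL SD or correlation. The validity of the HRQOL comparison is not in question, and the other efficacy endpoints are untouched.

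**What to change.** In SAP 10.7, for the initial model:

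- Name the pre-randomization questionnaire as the HRQOL baseline, taking precedence over SAP 7.6, and not a Cycle 1 Day 1 score taken after assignment.
- State that week 0 is in the response vector and drop the treatment main effect, keeping week and week-by-treatment, so that both arms share one baseline mean. The alternative is post-baseline scores with baseline and baseline-by-week as covariates, which loses patients who have only a baseline score.
- Add the three Amendment 3 factors as fixed effects, using the corrected values as in the primary efficacy analysis.
- Use the same specification for every QLQ-C30 scale.

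Do not impose the common mean within the dropout groups of the pattern-mixture model. The small downside is that the two models would then differ in baseline handling as well as in the missing-data assumption. Report the initial model without the constraint beside the pattern-mixture result, so that the like-for-like comparison is kept.

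The cost is SAP wording, modest programming and one extra model fit per scale. It needs no new data or patients, and no other endpoint changes.

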5 SAMPLE SIZE CALCULATION

The primary efficacy endpoint is progression free survival (PFS). For patients with metastatic advanced GPNMB-expressing breast cancer in the treatment setting under investigation, median PFS of 4 months is anticipated following randomization to capecitabine. It is hypothesized that CDX-011 will increase median PFS in such patients by 2.25 months (i.e., 4.0 vs 6.25 months). Under the assumption of proportional hazards, such an increase corresponds to a hypothesized hazard ratio of 0.64. If this hypothesized hazard ratio is true, 203 PFS events (total of two arms) determined by IRC will provide 85% power with 2-sided type I error of 0.05. Under the assumption of exponential distribution for each arm and uniform enrollment over 2 years, and 10% drop out rate (PFS events cannot be observed), 300 patients (200 in the CDX-011 arm and 100 in the capecitabine arm) are needed, and it is anticipated that 203 PFS events will be observed in approximately 26 months from the date the first patient is randomized. The sample size calculation is performed using SAS v9.4.

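### The HRQOL pattern-mixture rule counts patients still being assessed at the data cutoff as dropouts if they were randomized less than 6 months earlier

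*SAP*

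**What the plan says.** SAP 10.7 plans a pattern-mixture model as a sensitivity analysis to the main HRQOL mixed model. Patients are "stratified into groups based on their treatment arm and timing of study dropout". A patient is a dropout "if their last HRQOL assessment was prior to 6 months" and a completer otherwise. There is no exception for a patient whose assessments are still running when the data are cut.

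A mixed model is fitted in each stratum. The text expects this to yield a treatment effect for dropouts and another for completers, and it combines the strata into a weighted average per treatment arm. The general description earlier in the same section speaks of an average over the whole study population. Neither the between-arm contrast nor the weights are written out.

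The stated rationale is that dropout will come mostly from progression and death. Characteristics of dropouts and completers are also to be compared, to judge whether the data are missing at random (MAR).

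HRQOL is collected at baseline, on Day 1 of odd cycles (every 6 weeks) and at End of Treatment. No HRQOL cutoff or minimum follow-up is given. The only equation of 6 months with 24 weeks is in the disease-assessment schedule and footnote c of SAP Table 3, not in the HRQOL rule.

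SAP 5 assumes "uniform enrollment over 2 years" and expects the required PFS events about 26 months after the first randomization. SAP 10.1 and 10.7 make HRQOL exploratory, with nominal p-values.

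**The concern.** A pattern-mixture model is informative only if its patterns separate patients whose data are missing for different reasons. SAP 10.7 itself warns that ignoring those reasons can bias the estimates, and then defines its patterns by timing alone. Accrual runs to month 24 and the cutoff is expected near month 26, so the last patients enrolled cannot have a 6-month assessment however well they are doing. They enter the stratum that is meant to represent progression and death.

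If CDX-011 works as hypothesized, more of its late enrollees are still on treatment at the cutoff, so the mixing is uneven between arms. Two outputs are at stake: the dropout-specific HRQOL estimates, and the dropout-versus-completer comparison on which the MAR judgement rests.

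**Working it through.** **Inputs.**
- SAP 5: "300 patients (200 in the CDX-011 arm and 100 in the capecitabine arm) are needed"; medians "i.e., 4.0 vs 6.25 months", capecitabine first; exponential PFS; accrual uniform over 24 months; 10% loss of PFS events; cutoff at about month 26.
- SAP 4.1: 2:1 allocation.
- Assumed, because the documents do not say: the HRQOL cutoff is the PFS cutoff, time to progression stands in for time under HRQOL assessment, and all 300 patients contribute HRQOL data.

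**1. The plan's own figures.** The plan says "203 PFS events (total of two arms) determined by IRC will provide 85% power with 2-sided type I error of 0.05". With HR = 4.0/6.25 = 0.64, Schoenfeld's formula gives (1.960 + 1.036)² / [(2/3)(1/3)(ln 0.64)²] = 203 events, with power 0.850.

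For timing, the hazards are ln 2/6.25 = 0.1109 and ln 2/4 = 0.1733 per month. The event probability by month 26 is 1 − [exp(−2λ) − exp(−26λ)]/(24λ), which is 0.720 for CDX-011 and 0.833 for capecitabine. That is 227.3 events before losses and 0.9 × 227.3 = 204.5 after. The 203rd event falls at month 25.8. Both stated figures are reproduced.

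**2. Patients who cannot be completers.** Those randomized in months 20 to 24 have 2 to 6 months of possible follow-up: 300 × 4/24 = 50 (33.3 CDX-011, 16.7 capecitabine).

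**3. Of these, patients still progression-free at the cutoff.** The mean of exp(−λt) over t = 2 to 6 is:
- CDX-011: (0.801 − 0.514)/(0.1109 × 4) = 0.647, and 33.3 × 0.647 = 21.6 patients.
- Capecitabine: (0.707 − 0.354)/(0.1733 × 4) = 0.510, and 16.7 × 0.510 = 8.5 patients.

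Together about 30 are mislabelled. The other 20 or so have already progressed or died and are rightly called dropouts.

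**4. Share of each dropout stratum.** Completers are those randomized at least 6 months before the cutoff (20/24 of each arm) and still under assessment at 6 months.
- CDX-011: completers 200 × 20/24 × 0.514 = 85.7; dropouts 114.3; share 21.6/114.3 = 18.9%.
- Capecitabine: completers 100 × 20/24 × 0.354 = 29.5; dropouts 70.5; share 8.5/70.5 = 12.1%.

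**5. Range.**

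| Cutoff | Meaning of 6 months | Cannot be completers | Mislabelled |
|---|---|---|---|
| Month 26 | 24 weeks (5.52 months) | 44 | about 27 |
| Month 26 | 6.0 months | 50 | about 30 |
| Month 26 | week-30 visit (6.90 months) | 61 | about 35 |
| Month 28 | 6.0 months | 25 | about 13 |
| Month 30 | 6.0 months | 0 | 0 |

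The third row is a realistic reading. Six calendar months are about 26.1 weeks, and an on-schedule week-24 visit falls at the latest at 24 weeks plus 5 days. Under a calendar reading, a patient without delays becomes a completer only at the week-30 visit or through a later End of Treatment visit.

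**6. Effect on the estimates.** This is an illustrative simulation of 400 runs; its slopes are assumed and are not in the documents. HRQOL changes by −2.5 points/month if time on treatment is under 6 months and by −0.5 otherwise, with +0.5 for CDX-011 in both patterns. The true arm difference is 0.5 + 2 × (0.514 − 0.354) = 0.82.

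| Quantity (points/month) | With cutoff truncation | Without |
|---|---|---|
| CDX-011 dropout slope | −1.50 | −2.00 |
| Capecitabine dropout slope | −2.20 | −2.51 |
| Arm difference among dropouts | 0.70 | 0.51 |
| Combined arm difference | 0.825 | 0.843 |

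The simulation standard error of the combined difference is 0.023. In this scenario the dropout-specific results move and the combined contrast hardly does.

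**The case against.** **Stratifying by arm.** A reader might infer that forming strata by arm defeats the analysis, because a model inside one arm contains no treatment term. The documents do not support that. Each arm-by-pattern model gives an arm-specific slope. Differencing the arms within a pattern gives the pattern-specific effect, and weighting each arm's slopes by its own pattern shares gives the overall one. The per-arm weighted average in SAP 10.7 points to exactly this, and the simulation recovers 0.825 against a true value of 0.82. What stands is a gap in wording: the contrast and weights are not stated, and the two descriptions of the average differ.

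Pooling the pattern weights across arms would be no improvement. In the illustrative scenario it would return only 0.5, losing the part of the treatment effect that acts through who drops out.

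**Failure or false reassurance.** A reader might also infer that the sensitivity analysis cannot serve its purpose, or that it errs towards reassurance. Its purpose is to compare treatment effects across missing-data assumptions, and no material shift in the combined contrast was found. That is one scenario, so it does not prove robustness either.

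**Size.** Fifty is the number who cannot be completers, not the number mislabelled. Month 26 is a planning forecast. HRQOL covers a subset: patients fluent in a language with a validated questionnaire who also completed it at baseline. Stopping for toxicity or by choice is ignored. For a given cutoff and threshold the counts are therefore upper bounds.

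**Importance.** The main HRQOL model does not use the dropout label, and purely administrative truncation is compatible with its MAR assumption. All of these limits stand. None removes the fact that the rule has no place for a patient still being assessed at the cutoff.

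**Conclusion.** The concern holds in a limited form. The rule mixes administratively censored patients with those who stopped because of progression or death. On the plan's design figures about 30 patients are affected, unevenly by arm (18.9% against 12.1% of the dropout strata), with a range of 0 to about 35. The figures rest on uniform accrual, a shared PFS and HRQOL cutoff near month 26, PFS as a proxy for time under assessment, and full HRQOL participation.

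The consequence is blurred dropout-specific estimates and a blurred MAR check. It is not a demonstrated bias in the overall HRQOL comparison, and the primary PFS analysis is untouched. This is a desirable correction to an exploratory analysis, not a serious defect.

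**What to change.** Amend SAP 10.7 as follows:

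- Class as dropouts only patients whose HRQOL assessments ended before 6 months for a reason other than the data cutoff.
- Put patients still under assessment at the cutoff who have not reached 6 months in a separate, administratively censored group. Alternatively, limit this sensitivity analysis to patients randomized early enough to have reached the 6-month visit by the cutoff.
- Define 6 months in weeks, and say whether the week-24 or the week-30 visit makes a completer.
- Keep the arm-by-pattern strata and arm-specific weights. State that the treatment effect is the between-arm difference of the arm-specific estimates, within each pattern and overall, and align the two descriptions of the weighted average.

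The cost is a few lines of SAP text and a small programming change. The downside is slightly smaller strata, or one more stratum per arm, in an exploratory analysis.

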Mixed effects models for repeated measures data based on maximum likelihood theory provide valid results when data are missing at random (MAR). Data are MAR if they depend on the observed data only. If the probability of missing depends on the unobserved HRQOL scores, then the missing data are considered non-ignorable, or missing not at random (MNAR). This type of missing data can occur in association with death, disease progression, or toxicity. Distinguishing between MAR and MNAR is not trivial and relies on assumptions that are themselves untestable because the required data are missing. Applications of mixed models have been developed that can assist in the analysis of non-ignorable missing data. One such application is the pattern-mixture models. In this method, patients are stratified by the missing data pattern, and mixed models are created within each stratum. Parameter estimates for each stratum are then combined into a weighted average for the entire study population.

The pattern of missing HRQOL data in this study will be examined with patients classified into groups based on the timing of study dropout for purposes of future HRQOL assessment. The chi-square test and two-sample t-test, as appropriate, will be used to compare baseline characteristics between dropout groups. Because it is not possible to definitively determine whether missing data are ignorable, sensitivity analyses

(comparing the mixed effects model and pattern-mixture model, described below) will be performed to ensure that treatment group effects are consistent across different analytical methods with different missing data assumptions and to evaluate the range of possible treatment group differences.

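### SAP 10.7 compares dropouts with completers at baseline to evaluate MAR, but that comparison can only show departure from MCAR and cannot separate MAR from MNAR

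*SAP*

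**What the plan says.** All the relevant text is in SAP 10.7.

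- **Definitions.** For MAR: "Data are MAR if they depend on the observed data only". For the alternative: "If the probability of missing depends on the unobserved HRQOL scores, then the missing data are considered non-ignorable", that is, MNAR.
- **Testability.** "Distinguishing between MAR and MNAR is not trivial and relies on assumptions that are themselves untestable because the required data are missing".
- **Tests on dropout groups.** To examine the pattern of missing data, "The chi-square test and two-sample t-test, as appropriate, will be used to compare baseline characteristics between dropout groups".
- **Why two models are run.** "Because it is not possible to definitively determine whether missing data are ignorable, sensitivity analyses" will compare the mixed model with the pattern-mixture model.
- **Initial model.** A linear mixed model with patient as random effect and treatment, linear time and their interaction as the fixed terms. Its missing-data assumption is stated: "This model, which assumes missing data are MAR".
- **Purpose of the baseline comparison.** After describing the pattern-mixture model, the section adds: "As noted previously, selected demographics and disease characteristics also will be summarized for" dropouts (last assessment before 6 months) and completers (6 months or later), "separately to evaluate if the missing HRQOL data are MAR".

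SAP 10.1 and 10.7 both class HRQOL as exploratory, with nominal p-values.

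**The concern.** The last statement gives the comparison a job that it cannot do. Demographics and disease characteristics at baseline are observed. If they differ between dropouts and completers, missingness depends on observed data, which the SAP's own definition allows under MAR. If they do not differ, missingness may still depend on scores that were never recorded. The hypothesis actually examined is that dropout is unrelated to the measured baseline variables, which is a consequence of MCAR. The purpose clause therefore conflicts with the untestability statement earlier in the same section.

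Two things are at stake, both within HRQOL:

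- A table with few differences, labelled as an evaluation of MAR, could be read as support for the mixed model.
- The useful product of the comparison is left unused. Baseline factors that predict both dropout and quality of life belong in the model, and the SAP does not put them there.

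**Working it through.** The SAP gives no figure on this point, so there is none to reproduce. The design medians are used in step 2. They agree with the stated design: 4.0/6.25 = 0.64, and the Schoenfeld formula at 2:1 allocation, two-sided 0.05 and 85% power gives 203 events, as in SAP 5.

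**1. What each result implies.** Let D be dropout, X the measured baseline characteristics, Yo the recorded scores and Ym the unrecorded scores.

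- MCAR: D depends on none of these.
- MAR: D depends on X and Yo only.
- MNAR: D still depends on Ym, given X and Yo.

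The chi-square and t-tests have the null that D is independent of X.

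| Result | MCAR | MAR | MNAR |
|---|---|---|---|
| X differs by D | contradicted | compatible | compatible |
| X does not differ | compatible | compatible | compatible |

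The MAR and MNAR columns are identical.

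**2. How much dropout to expect.** Assume exponential PFS, as in SAP 5, and HRQOL dropout that tracks progression. The proportion progression-free at 6 months is then:

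- capecitabine: 2^(-6/4.0) = 35%
- CDX-011: 2^(-6/6.25) = 51%
- pooled 2:1: (2 × 51.4 + 35.4)/3 = 46%

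So about 54% would be dropouts. The simulation in step 3 uses about 50%.

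**3. Size of the effect.** A two-sample t-test of one standardised baseline variable x was simulated, dropouts against completers, with 4,000 replicates. N was 300 or 200, because the SAP does not give the size of the HRQOL subset. The two-sided level was 0.05, an assumption: the SAP sets no level for these tests, and 0.05 is its nominal level for HRQOL p-values. The later score was u = ρx + √(1 − ρ²)e, with e standard normal. Dropout followed logit P(D) = −bx or −bu. The values of b (log-odds per SD) and ρ are assumptions.

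- MCAR: about 5% rejections at either N.
- MAR through x: 92% (N = 200: 79%) at b = 0.4, and 100% (100%) at b = 0.8.
- Dropout through u, N = 300:

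| b | Status of u | ρ = 0 | 0.3 | 0.5 | 0.7 |
|---|---|---|---|---|---|
| 0.8 | recorded (MAR) | 5% | 45% | 87% | 99% |
| 0.8 | unrecorded (MNAR) | 5% | 44% | 86% | 99% |
| 0.4 | recorded (MAR) | 5% | 16% | 38% | 64% |
| 0.4 | unrecorded (MNAR) | 5% | 17% | 38% | 67% |

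At N = 200 and b = 0.8 the rows are 5%, 31%, 71%, 94% (MAR) and 5%, 32%, 70%, 95% (MNAR). Each pair of rows estimates the same quantity. The test sees only x and D, and their joint distribution does not depend on whether u was recorded. Differences within a pair are simulation noise.

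**4. Why the model's covariates matter.** The mixed model is protected only against dropout that depends on variables it contains. A baseline factor outside the model that predicts both dropout and the course of the score can bias it, even when the data are MAR in the SAP's sense. In a small simulation with dropout driven by such a factor (assumed inputs, 60 replicates, some convergence warnings), adding the factor moved the control-arm slope from −1.24 to −1.97 (truth −2). The spurious treatment-by-time effect moved from −0.53 to −0.14 (truth 0). This shows the direction of the effect. It does not estimate the bias in this trial.

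**The case against.** The strongest defence is that the SAP never acts on this comparison. Its verbs are to summarise and to evaluate. No threshold, model choice or conclusion is tied to the result. The tests appear in an earlier paragraph, where their purpose is to examine the pattern of missing data, and that purpose is legitimate. The SAP says openly that ignorability cannot be settled, and for that reason it runs the pattern-mixture model whatever the comparison shows. HRQOL is exploratory. All of this stands, and it keeps the point small. It does not rescue the purpose clause, which names a question that the comparison cannot answer.

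A reader might infer three stronger claims. The documents support none of them.

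- *The SAP decides between MAR and MNAR by this test.* It contains no such decision step.
- *The comparison misleads in both directions, rejecting under MAR and staying silent under MNAR.* Neither half is general. It is silent under MNAR only when the compared baseline variables are unrelated to the unrecorded scores. Otherwise it rejects about as often as under MAR (44% to 99% in the table for b = 0.8). Under MAR it rejects only when dropout runs through, or is correlated with, those variables.
- *The HRQOL results would be overstated by about 10 points, the SAP's threshold for a meaningful change.* A figure of that size arises for the raw mean change within an arm, under an assumed MNAR mechanism with heavy dropout. It is not a bias in the planned treatment comparison. It comes from the dropout and would remain if the clause were deleted.

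**Conclusion.** The purpose given for the dropout/completer comparison is wrong and conflicts with the SAP's own account of MAR and MNAR. The comparison can show departure from MCAR and nothing further. That conclusion follows from the definitions. The simulated percentages illustrate it and rest on assumed effect sizes, correlations and dropout.

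The point is minor. It is an error of wording and interpretation, together with a mixed model that leaves out prognostic covariates the trial already collects. The size of any resulting bias in this trial cannot be derived from the documents. PFS, ORR, OS, the type I error control and the sample size are unaffected.

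**What to change.** In SAP 10.7:

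1. Replace the purpose clause ("separately to evaluate if the missing HRQOL data are MAR") with a statement that the summary describes whether dropout is related to measured baseline characteristics (departure from MCAR). State that nothing about MAR versus MNAR will be concluded from it.
2. Prespecify prognostic baseline covariates, with their time interactions, in the HRQOL mixed model. Candidates already collected are ECOG status, visceral disease and the three stratification factors. Name them in advance, because choosing them by their observed association with dropout would be data-driven. This makes MAR, given the model, more plausible.

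The cost is a wording change, some programming and a few parameters. Five binary covariates, each with a main effect and a time interaction, add 5 × 2 = 10. No new data, visits or patients are needed.

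A delta-adjusted analysis of global health status, with a stated rule for deaths, would be an optional supplement. The SAP already plans a pattern-mixture model for potentially non-ignorable missingness, so this addition is not a correction.
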